22.2 Evaluations

All AEs, serious and non-serious, should be recorded in the CRF. If no AE has occurred during the study period, this should also be recorded in the CRF.

The following evaluations are to be done by the Investigator in connection with the AE:

- type of event
- seriousness
- degree of severity
- duration (start end)
- action taken
- causality with study product
- outcome of the adverse event

For AE reporting purposes no distinction should be made between the IP and any reference/comparator product.

22.3 Reporting of SAEs

All SAEs must be reported by the Investigator using phone or fax within 24 hours of knowledge of the event to the Monitor or other members of the staff at the CRO Icon, regardless of the time that may have elapsed from the time the event occurred to when the Investigator first learns of it. The Initial Report should contain as a minimum the following information:

- subject identification
- treatment specification
- adverse event diagnosis
- time specification for the medical event
- name of the original reporter

A Serious Adverse Event Report Form must also be completed, signed by the Investigator and submitted to the CRO Icon no later than five calendar days after the initial information was received. Apart from the information above, this Follow-up Report should also contain the following information:

- assessment of severity
- assessment of causality

No distinction should be made between the IP and the reference product regarding reporting of SAEs as long as the code is not broken.

SAEs should be reported to the CRO Icon even after the clinical study has been finished, if, in the judgment of the Investigator, there might be an association between the event and the previous use of the study product(s) or as a result of the study procedures. This post-study observation period will be up to 30 days after administration of last dose of study product.

An SAE may qualify for reporting to the FDA by the Sponsor or Sponsor's representative if the AE is both serious and unexpected based upon the current Investigator's Brochure. In this case, all Investigators will receive a formal notification describing the SAE in the form of an IND safety report.

22.4 Exceptions from expedited reporting of SAEs

An event need not to be reported as an SAE if it represents only a relapse or an expected change, or progression of a pre-existing condition and is without any other symptoms or signs than those present before treatment. This event needs only to be reported as an AE and should be described in the Study Protocol.

22.5 Follow-up period after an AE

If a study patient is withdrawn due to an AE, or if an AE persists at the end of the study treatment period, this should be followed up by a physician until the condition has ceased or until the subject is under professional medical care and a potential causality between the investigational drug and the AE has been penetrated. An outcome assessment should be performed when an AE persists.

22.6 Procedures in case of pregnancy

In case of pregnancy or suspicion of possible pregnancy, the study treatment must be stopped immediately, and the patient discontinued from participation in the study. Pregnancy itself is not regarded Albireo 37(89) 07 June 2010

as an AE unless there is a suspicion that the IP may have interfered with the effectiveness of the contraceptive medication. However, the outcome of all pregnancies (spontaneous miscarriage, elective termination, normal birth or congenital abnormality) must be followed up and documented even after the patient was discontinued from the study.

All events of congenital abnormalities/birth defects are SAEs. Spontaneous miscarriages should also be reported and handled as AEs. All outcomes of pregnancy must be reported to the CRO Icon on the pregnancy outcomes report form.

22.7 Procedures in case of overdose

Overdose is defined as any dose greater than the highest daily dose in the protocol-defined doses, ie, 20 mg. Any overdose must be recorded in the study medication section of the CRF. At least 12 hours should elapse between consecutive calendar days and no more than one dose should be taken per calendar day. In case of overdose, appropriate treatment should be given and hospitalization for observation should be considered. Though an overdose may not be considered an SAE, any case of reported overdose must be reported to the sponsor and CRO in the same expedited manner as an SAE using an SAE form. If the PI and/or sponsor and CRO consider the overdose to be medically significant, it would then be reported as an SAE.

23 DATA QUALITY ASSURANCE

23.1 Monitoring and auditing procedures

The study site will be visited by the Monitor and/or the Project Manager periodically at times agreed on by the Investigator and the Monitor. It is the function of the Monitor to ascertain that all aspects of the Study Protocol are complied with and that the conduct of the study conforms to applicable regulatory requirements and established rules for Good Clinical Practice (GCP).

At the time of each monitoring visit, the Monitor will review the completed CRFs to ascertain that all items have been completed and that the data provided are accurate and obtained in the manner specified in the protocol.

The Monitor will also check that the data in the CRF are consistent with the clinical records (Source Data Verification) and that study results are recorded completely and correctly. The Monitor will check on the reporting of SAEs and the procedures for IP accountability and record keeping. For this purpose the Monitor must be given direct access to clinical records, original laboratory data, etc., as far as these relate to the study and without jeopardizing subject integrity. CRFs for all included subjects must be made available to the Monitor for review.

The study site may also be subject to quality assurance audit by the Sponsor or someone appointed for this task by the Sponsor. A Regulatory Authority may request to make an inspection of the study site. The procedures of such a visit would be similar to those of a monitoring visit, and data already checked by the Monitor may be checked again. The Investigator is required to inform the Sponsor immediately of an inspection requested by a Regulatory Authority.

23.2 Case Report Forms (CRFs)

CRFs of a design mutually agreed upon by the Sponsor, the CRO and the PI will be developed by the Mayo Clinic.

A CRF must be completed and signed for each included subject. All data and information on the CRFs are to be neatly and legibly recorded in black or blue ball-point ink to ensure legibility of self-copying and photocopied pages. Corrections on the CRFs must be made by one single line through the incorrect data, leaving the corrected data clearly visible. The revised entry should be made alongside, initialed and dated by a member of the PI's research team who is authorized to initial CRF changes for the Investigator. This authorization must be documented in writing. Correction fluids are not permitted.

The completed CRFs should be made available for checking of completeness and accuracy before collection by the Monitor as agreed in advance. The original CRFs are the sole property of the Sponsor and should not be copied or made available in any form to a third party, with the exception of authorized representatives of local Regulatory Authorities, without the written permission from the Sponsor.

23.3 Source Data

Source documents will be the Mayo Clinic EMR, original laboratory results and original electronic data generated from the scintigraphic investigations. Relevant EMR for study patients will be printed in certified hardcopies prior to the monitoring visit and used for SDV.

The extent of SDV to be performed will be described in the study specific monitoring instructions prior to initiation of the study.

The source of derived information appearing in the CRF will be included in each individual CRF binder for monitoring purposes. The SDV process will be performed continuously during the monitoring visits at the clinic.

23.4 Training of study staff

It is the responsibility of the PI to ensure that all personnel involved in the study are fully informed of all relevant aspects of the study, and have a detailed knowledge of and training in the procedures that are to be executed by them.

All Investigators and staff carrying out observations of primary or other major efficacy variables involved in the study should provide a Curriculum Vitae (CV). The PI will keep a list of all personnel involved in the study together with their function and study related duties delegated. He/she will ensure that appropriate study related training is given to all of these staff, and that any new information of relevance to the performance of this study is forwarded to the staff involved.

Before inclusion of subjects the Monitor and/or Project Manager will perform a study initiation visit to inform and train relevant study staff.

24 STATISTICAL METHODS

24.1 Statistical considerations

An analysis of covariance (ANCOVA) will be used to compare transit parameters and patient bowel pattern diary summaries (i.e., stool frequency, mean stool consistency and mean ease of passage scores) among the treatment groups. The covariates considered for inclusion in the analyses are age, body mass index (BMI) and the corresponding baseline (pre-treatment) bowel pattern diary summaries. If necessary a suitable transformation for potential skewness in the distributions of measured responses or heterogenous variation amongst the treatment groups may be used (i.e., ANCOVA on ranks or square root transformed stool frequency.

If the ANCOVA test for overall treatment effects for a given response has a p value less than or equal to 0.10, then both the 15 mg and 20 mg doses will be compared to placebo using Dunnett's Test.

Since each of the primary endpoints assesses a separate hypothesis regarding the effects of A3309, no adjustment in the alpha level for testing multiple types of endpoints is anticipated, and a two-sided significance level of 0.05 will be used in each ANCOVA model.

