Since each of the primary endpoints assesses a separate hypothesis regarding the effects of A3309, no adjustment in the alpha level for testing multiple types of endpoints is anticipated, and a two-sided significance level of 0.05 will be used in each ANCOVA model.

Statistical Power

Based on data acquired using the same methods in the laboratory, the sample size of 12 patients per group provides 80% power to detect differences of approximately 27% to 37% in colonic transit, the primary endpoints. This magnitude of change is considered clinically significant.

Pharmacokinetic and Pharmacodynamic analyses

Plasma concentration of A3309 vs time curves will be plotted for each subject, on both linear/linear and log₁₀/linear scales. Mean plasma concentration vs time curves will also be presented by dose, PK and PD parameters.. Exploratory analyses of the PD variables will be conducted and described in the Statistical Analysis Plan (SAP).

Efficacy analyses

Exploratory analyses of the efficacy variables will be conducted and described in the Statistical Analysis Plan (SAP).

Analysis data sets

The primary analyses will follow the intent to treat (ITT) paradigm with all patients randomized included in the analyses. Those patients with missing response values will have their missing values imputed via the overall (patients with non-missing data) mean and a corresponding adjustment in the ANCOVA residual error variance degrees of freedom (subtracting one for each missing value imputed).

Safety data will be presented for all patients receiving investigational product.

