11 OVERALL STUDY DESIGN AND SCHEDULE OF EVENTS

11.1 Study Design

This is a single-center, randomized, parallel group, double-blind, placebo-controlled, dose response, pharmacodynamic and pharmacokinetic study to evaluate the effects A3309 on gastrointestinal and colonic transit in patients with functional constipation. Patients with functional constipation will be screened for eligibility and informed about the study during pre-screening dialogue and also at the initial Visit 1 screen.

Within seven (7) to fourteen (14) days of Visit 1, eligible patients will return for an abbreviated scintigraphy test with images obtained only at 4 and 24 hours post In¹¹¹ capsule ingestion. A geometric center at 24 hours must be less than 2.30, the median of normal colonic transit in normal healthy volunteers (as determined by analysis of a compilation of prior [name] studies), to qualify for randomization to study medication, either 15 or 20 mg A3309 or placebo administered orally once daily for fourteen (14) consecutive days. The allocation to treatment group will be concealed.

A urine pregnancy test will be performed for all females of child bearing potential at Visit 1 and again within the 48 hours prior to the receipt of radiation for both the abbreviated and post-study medication transit scintigraphy tests at Visit 2 and Visit 4. Note that females who are status post bilateral tubal ligation, hysterectomy or postmenopausal are exempted from this test.

Study medication will be administered at the Charlton 7 Clinical Research Unit (CRU) at Visit 4, 5, and 6, the days of scintigraphic assessment of gastric, small bowel and colonic transit of solids performed over a 48 hour period.

Within seven (7) to ten (10) days of Visit 6, patients will return to the Charlton 7 CRU for final safety monitoring and an exit physical examination and interview with study staff.

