Within 7-14 days of Visit 1, patients will return to Charlton 7 CRU fasting for the previous eight hours, no food or drink allowed. Vital signs (pulse, blood pressure, respiration rate and temperature) will be measured. They will be given a capsule containing a small amount of In¹¹¹ radioactivity and asked not to eat anything for the next two hours and to return four hours later for one five minute camera picture. Patients will return the following morning at the same time the capsule was taken for one final five minute camera image. If the camera indicates a state of constipation by showing a geometric center at 24 hours to be less than 2.30, , the median of normal colonic transit in normal healthy volunteers (as determined by analysis of a compilation of prior [name] studies ,the patient will continue in the study and be randomized to the study medication. If the camera does not indicate a state of constipation by showing a geometric center equal to or greater than 2.30, the patient will end the study at this time.

Visit 3 Randomization and Administration of Study Medication

The patient will complete a six question survey of constipation symptoms and treatment efficacy at the end of the pre-treatment period, before receiving study medication. The patient will then be randomized to a dose of the study medication which is either a placebo (an inactive substance) or a 15 mg or 20 mg dose of A3309 study medication taken orally once daily for a total of fourteen consecutive days, eleven doses at home and three at the Charlton CRU during the final transit scintigraphy test, Visit 4 to Visit 6. Patients will dose at home and record the dosing of study medication in their Bowel Pattern Diaries.

Prior to Visit 4

Females of child bearing potential must have a negative urine pregnancy test performed within forty-eight hours prior to receipt of radiation in the abbreviated transit scintigraphy test. Females who have experienced a bilateral tubal ligation, hysterectomy or menopause will not need the pregnancy test.

Visit 4 Final Transit Scintigraphy and Pharmacokinetic Sampling

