20 RANDOMIZATION METHODS

Randomization will be stratified on BMI ($< 25, > = 25 \text{ kg/m}^2$). IP doses will be randomly assigned in fixed block sizes according to a schedule provided by the study statistician. Mayo Clinic Research Pharmacy will maintain the randomization schedule.

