24.5 Transit data analysis

A variable region of interest program is used to quantitate the counts in the stomach and each of four colonic regions: ascending, transverse, descending, and combined sigmoid and rectum. These counts were corrected for isotope decay, tissue attenuation, and downscatter of ¹¹¹ In counts in the ^{99m}Tc window.

Data will be analyzed as in previous studies.

1. Geometric mean of counts in anterior and posterior gastric regions of interest will be used to estimate by power exponential analysis of the proportionate emptying over time of counts from ^{99m}Tc solids and ¹¹¹In from the stomach. The proportion of ^{99m}Tc and ¹¹¹In reaching

the colon at 6 hours will also be estimated as a measure of orocecal (and a surrogate for small bowel) transit.

- 2. Geometric center of colonic counts for solids at 4, 24 and 48 hours will be estimated using geometric mean of counts in ascending, transverse, descending and rectosigmoid colon and stool (weighted by factors of 1 to 5 respectively). The primary variable of interest in overall colonic transit is the geometric center at 24 hours.
- 3. Ascending colon emptying t1/2 will be estimated by power exponential analysis of the proportionate emptying over time of counts from the colon. The primary data for this analysis will be the proportion of decay and depth-corrected counts in the ascending colon on the hourly scans on the first day of transit measurement and the 24 h data.

The primary summaries obtained for comparison of transit profiles will be the colonic geometric center at 24 hours and the ascending colon emptying $t\frac{1}{2}$. The geometric center is the weighted average of counts in the different colonic regions: ascending (AC), transverse (TC), descending (DC), rectosigmoid (RS), and stool. At any time, the portion of colonic counts in each colonic region is multiplied by its weighting factors as follows: (%AC x 1 + %TC x 2 + %DC x 3 + %RS x 4 + %stool x 5)/100 = geometric center. Thus, a high geometric center implies faster colonic transit. A geometric center of 1 implies that all isotope is in the ascending colon and a geometric center of 5 implies that all isotope is in the stool. The $t\frac{1}{2}$ of ascending colon emptying is also estimated by plotting the activity-time curve for percent residing in the ascending colon; linear interpolation is used to connect points.

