24.6 Stool frequency and stool consistency

Patients are asked to keep a daily bowel pattern diary documenting the number of stools and the consistency (Bristol Stool Scale (28)) of each stool. These are averaged as number of bowel movements or consistency of bowel movements per day per patient. Number of bowel movements and consistency are subsequently averaged over the study periods (i.e. run-in and treatment) per patient. The ANCOVA will be used to assess treatment effects on each of these two measures separately, using the corresponding run-in values as covariates. In addition, treatment effects on specific constipation symptoms, considered as discrete categorical responses, will be evaluated by a contingency table analysis of the post-treatment responses based on the final post-treatment bowel pattern diaries and questionnaires concerning constipation symptoms and treatment efficacy.

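### The primary GC24 model does not name the Visit 2 GC24 that every eligible randomised patient already has, and leaves BMI, the randomisation stratum, optional

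*Combined protocol and SAP*

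**What the plan says.** Section 24.1 and the synopsis (Statistical methods) apply one ANCOVA to the transit parameters and the diary summaries. On covariates they say: "The covariates considered for inclusion in the analyses are age, body mass index (BMI) and the corresponding baseline (pre-treatment) bowel pattern diary summaries". If the overall treatment test gives p of 0.10 or less, "then both the 15 mg and 20 mg doses will be compared to placebo using Dunnett's Test".

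The primary endpoint is GC24 on treatment (sections 9.2 and 24.4). A pre-treatment value of the same variable exists. Section 11.1 makes it a condition of randomisation: "A geometric center at 24 hours must be less than 2.30". Section 11.3 (Visit 2) describes how it is obtained: "Patients will return the following morning at the same time the capsule was taken for one final five minute camera image".

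Section 20 says "Randomization will be stratified on BMI", with categories below 25 and 25 or more kg/m². For stool frequency and consistency, section 24.6 commits to adjustment "using the corresponding run-in values as covariates". Section 24.5 makes no such commitment for transit. Its sentence "Data will be analyzed as in previous studies" introduces the image quantification and gives no model. The synopsis sends only exploratory efficacy analyses to a SAP, and section 24.7 sends only the PK and PD analyses there.

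**The concern.** The plan adjusts two diary outcomes for their own baseline but makes no such statement for the primary outcome, although that baseline is measured before anyone is randomised. With 12 patients per arm, a prognostic baseline could add precision and would correct chance imbalance between arms.

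The list is also only of covariates to be considered. The primary test could be run with none, with age, with BMI, or with both, and BMI could enter as the stratum or as a continuous variable. Nothing in the text requires that choice before unblinding.

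Leaving out Visit 2 GC24 does not bias the randomised comparison. What is at stake is power, and one data-dependent choice in the primary analysis.

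**Working it through.** **Inputs from section 24.9.** GC24 CV 35%, difference 37%, 12 per group, two-sided 0.05. The correlation r between Visit 2 and final GC24 is not in the documents and is an assumption throughout.

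**The plan's own figure.** Section 24.9 states 80% power. Taking both percentages relative to the same mean, the standardised difference is 37/35 = 1.057. The two-sided t-test (22 df) gives 69.7%, and pooling the error over three arms (33 df) gives 71.0%. If instead the CV refers to the placebo mean and the 37% to a three-group mean with one arm shifted, the difference is 37/(1 − 0.37/3) = 42.2% of the placebo mean and power is 80.6% (22 df). Which mean is intended is a separate question. The plain reading is used below and the other reading is given at the end.

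**Formula.** Noncentral t with SE = 35 × √(1 − r²) × √f × √(2/12), where f allows for chance covariate imbalance. Two-sided Dunnett critical values (two comparisons, correlation 0.5) are 2.311 at 33 df, 2.317 at 31 df and 2.321 at 30 df.

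- No covariates: 33 df, f = 1.
- Age and BMI, neither prognostic: 31 df, f = 1 + 2/30, or 1 + 1/30 if stratification balances BMI.
- Visit 2 GC24 and BMI stratum: 31 df, f = 1 + 1/30.

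| Model | Power, pairwise 0.05 | Power, Dunnett | Difference detectable with 80% power, Dunnett |
|---|---|---|---|
| No covariates | 71.0% | 61.2% | 45.3% |
| Age + BMI, not prognostic | 68.1–69.4% | 58.0–59.5% | – |
| Visit 2 GC24 + BMI stratum, r = 0 | 69.4% | 59.5% | 46.1% |
| same, r = 0.3 | 73.5% | 64.0% | 44.0% |
| same, r = 0.4 | 76.8% | 67.8% | 42.3% |
| same, r = 0.5 | 81.3% | 73.1% | 39.9% |
| same, r = 0.7 | 93.2% | 88.8% | 32.9% |

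Break-even against no covariates is r of about 0.19 under either test. Dunnett power reaches 80% at r of about 0.60. Simulation (10,000 trials per r, 36 patients) gave Dunnett power of 0.583, 0.638, 0.728 and 0.884 at r = 0, 0.3, 0.5 and 0.7. Requiring the overall p ≤ 0.10 first changed nothing to three decimals.

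**Effect of the entry cut.** Selecting on GC24 < 2.30 narrows the baseline range. Assume bivariate normality, an unselected correlation ρ, and 50% to 90% of screened patients kept. The variance of the truncated standard normal baseline is v = 0.363 to 0.712, and r = ρ√v / √(1 − ρ² + ρ²v).

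| Unselected ρ | r after the cut | Dunnett power if CV 35% describes selected patients | Dunnett power if CV 35% describes unselected patients |
|---|---|---|---|
| 0.3 | 0.19–0.26 | 61.2% → 61.1–62.7% | 62.5–64.1% → 64.0% |
| 0.5 | 0.33–0.44 | 61.2% → 64.9–69.6% | 64.8–69.5% → 73.1% |
| 0.7 | 0.51–0.64 | 61.2% → 73.7–83.3% | 68.5–78.7% → 88.8% |

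The second reading matters because section 24.9 takes the CV from C-IBS studies and states no cut. The gain is similar under both: about 0 to 1.5, 4 to 8, and 10 to 22 points. A harsher set of normal assumptions takes an unselected 0.5 down to 0.24–0.30. At r = 0.30 the gain is 64.0 − 61.2 = 2.8 points.

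**Three-group-mean reading of the 37%.** Dunnett power is about 74% with no covariates, 76% at r = 0.3 and 84% at r = 0.5, and reaches 80% near r = 0.40.

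**The case against.** The strongest reply is that this shows silence and not a defect. A list of covariates to be considered is not exclusive, section 24.9 expects gains from important covariates without limiting which, and a SAP and earlier studies are mentioned that cannot be checked here. It is true that nothing shows Visit 2 GC24 would go unused. But neither reference is attached to the primary model, and a gain from unnamed covariates has not been secured.

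Section 20.1 keeps the statistician blinded until the analysis data set is final. That helps, but it does not require the model to be fixed by then.

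The size of the benefit rests on an unsupplied r, taken as common to all arms; a drug that changes transit could weaken it in the active arms. The two scans also differ. Visit 2 is abbreviated and timed from the capsule, while the final test uses standard meals and is timed from breakfast, which follows the capsule by an hour or more. All of this stands, and it is why a nil gain cannot be excluded.

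The comparison can be called uneven because age and BMI are taken as non-prognostic. If together they had a correlation of 0.3 with the outcome, the listed model would give about 64.0%, the same as the proposed one at r = 0.3. That is fair, and section 12.1 does regard body size as relevant. It supports fixing BMI in the model and does not argue against adding the outcome's own baseline.

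The BMI part is the weaker half. BMI is already listed, no precision gain from it can be quantified, and stratum versus continuous differed by at most 0.6 points in simulation.

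**Conclusion.** The concern holds. The documents make Visit 2 GC24 a condition of randomisation but do not name it for the primary model, and they do not say whether or how the BMI stratum enters that model.

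The consequence is possible loss of precision and an open model choice, not bias. Under Dunnett, with the entry cut allowed for under the 50% to 90% assumption, the gain is about nil at an unselected correlation of 0.3, 4 to 8 points at 0.5, and 10 to 22 points at 0.7. It could be smaller under harsher assumptions about the cut. The absolute power levels depend on how the 37% is read; the direction and rough size of the gain do not. The benefit is limited to GC24, because the abbreviated scan gives no baseline for gastric emptying, ascending colon emptying or GC at 48 h.

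The case for acting does not need a large r, since the possible cost is small and the data are already collected.

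**What to change.** In section 24.1 and the synopsis, state before unblinding that the primary GC24 model contains treatment, Visit 2 GC24 and BMI, with BMI as the randomisation stratum (<25, ≥25) or as continuous if so stated, and that the Dunnett contrasts come from this model. State whether age is in or out, and what would trigger the rank or other transformation that section 24.1 allows, so that the model is fully fixed.

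No new data are needed. Against no covariates, the change uses two error df (33 to 31). If neither covariate is prognostic, it costs about 1.8 points of Dunnett power (61.2% to 59.5% as rounded) or 1.6 points pairwise (71.0% to 69.4%). Against age plus BMI there is no extra df cost if Visit 2 GC24 replaces age. Keeping a non-prognostic age as well (30 df, f = 1 + 2/29) gives Dunnett power of 57.7%, 62.2%, 71.4% and 87.6% at r = 0, 0.3, 0.5 and 0.7.
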